8.5 AE Reporting and Follow-up

After initiation of study drug treatment, all AEs except for SAEs (Section 8.7 and 8.8) will be reported from the time of first study drug(s) administration until 100 (\pm 7) days after the last dose of all study treatment(s) (Safety Follow-up Visit 2) (see Section 5.5).

All ongoing nonserious AEs will be followed until resolution, the patient is lost to follow-up, patient death, or until the Safety Follow-up Visit 2 (or 100 [\pm 7] days after the last dose of study treatment). If the AE has not completely resolved by the last Safety Follow-up Visit, the final outcome of these ongoing AEs will be captured as "Not Recovered/Not Resolved" or "Recovering/Resolving", whichever is applicable.

For specific instructions on identifying and reporting SAEs, see Sections 8.6 and 8.7.

8.6 Serious AE Definition

An SAE is defined as any untoward medical occurrence that at any dose:

- Results in death.
- Is life-threatening, i.e., in the opinion of the Investigator, the AE places the patient at immediate risk of death from the event as it occurred; it does not include a reaction that, had it occurred in a more severe form, might have caused death.
- Requires inpatient hospitalization or prolongation of an existing hospitalization (for \geq 24 hours) that occurs during the course of a patient's participation in a clinical study, except for those due to the following:
 - A surgery or procedure that was planned before the patient entered the study and which is part of the planned study procedure.
 - Nonmedical reasons, in the absence of an AE (e.g., admit for overnight observation after the first dose of study drug, per Investigator judgment).
- Results in persistent or significant disability or incapacity.
- Is a congenital anomaly or birth defect.
- Is an important medical event that, based upon appropriate medical judgment, may jeopardize the patient and may require medical or surgical intervention to prevent one of the other outcomes listed above.

Death is an outcome of an AE and not an AE in itself. All events leading to death, regardless of relationship to study drugs, that occur during the protocol-specified reporting period, must be reported with the exception of deaths attributed to disease progression (refer to Section 8.9). An efficacy failure is not considered an SAE. “Life-threatening” means that the patient was at immediate risk of death from the event as it occurred. This does not include an event that might have led to death if it had occurred with greater severity. “Inpatient hospitalization” means the patient has been admitted to a hospital for medical reasons for any length of time. Additionally, if the patient presents and remains in the Emergency Room for more than 24 hours, the event will have met the inpatient hospitalization criteria. The Investigator should attempt to establish a diagnosis of the event based on signs, symptoms, and/or other clinical information. In such cases, the diagnosis will be documented as the AE and/or SAE and not the individual signs/symptoms.

8.7 Serious AE Reporting

Serious AEs occurring after the patient has provided informed consent, but before the first dose of study treatment or confirmed screen failure, will be collected as medical history unless the event is either new and attributed to protocol-mandated procedures by the Investigator or there is a significant change in the rate of occurrence or an increase in the severity of the pre-existing condition which is judged to be clinically important and attributed to the protocol-mandated procedures by the Investigator. Any new or clinically significant changes in the patient’s medical and/or cancer history that occur after the first dose of drug and meet the SAE criteria will be recorded as SAEs. All SAEs, regardless of causality or starting subsequent anticancer therapy, with an onset within 100 (\pm 7) days after the last dose of all study treatment(s) will be reported to Nektar Therapeutics Drug Safety immediately (i.e., no more than 24 hours after learning of the event).

In addition, all SAEs that occur beyond 100 (\pm 7) days after last dose of all study treatment(s) that are assessed by the Investigator as related to study drug(s) will also be reported to Nektar Therapeutics Drug Safety within 24 hours of awareness of the event.

All AEs and SAEs will be recorded in the electronic case report form (eCRF) database within the timelines outlined in the eCRF completion guideline. At the time of study start, SAEs may be reported using a paper SAE reporting form. During the study conduct, sites may transition to an electronic SAE (eSAE) system. Nektar or designee will provide training and account information prior to implementing an eSAE system at each site.

Electronic Serious Adverse Event (eSAE) Reporting Process

Site personnel record all SAE data in the eCRF database and from there transmit the SAE information to Nektar Drug Safety within 24 hours of the Investigator’s knowledge of the event. Detailed instructions can be found in the eCRF completion guidelines. If for any reason it is not possible to record the SAE information electronically, i.e., the eCRF database is not functioning, record the SAE on the paper SAE reporting form and submit within 24 hours of the

Investigator's knowledge of the event to Nektar Therapeutics Drug Safety via email or Safety Fax as listed at the beginning of this protocol.

As soon as it is possible to do so, any SAE reported via paper must be transcribed into the eCRF Database according to instructions in the eCRF completion guidelines. If an SAE has been reported via a paper form because the eCRF database has been locked, no further action is necessary.

For fatal or life-threatening events, copies of hospital case reports, autopsy reports, and other documents are also to be submitted by email or fax when requested and applicable. Transmission of such documents should occur without personal subject identification, maintaining the traceability of a document to the subject identifiers. Additional information may be requested to ensure the timely completion of accurate safety reports. Any medications necessary for treatment of the SAE must be recorded onto the concomitant medication section of the subject's eCRF and the event description section of the SAE form.

All SAEs will be followed as described in Section 8.8.

Reporting of SAEs to the IRB/IEC will be done in accordance with the standard operating procedures and policies of the IRB/IEC. Adequate documentation must be provided to Nektar Therapeutics, showing that the IRB/IEC was properly notified. Serious AEs will be reported by Nektar Therapeutics or designee to the Regulatory Authorities, per local regulations.

8.8 Serious AE Follow-up

All study treatment-related SAEs that have not resolved by the Safety Follow-up Visit 2 (or 100 [\pm 7] days after the last dose of study treatment) (Section 5.5) will be followed until any of the following occur (whichever comes first):

- The event resolves.
- The event has stabilized.
- The event returns to baseline, if a baseline value is available.
- It is unlikely that any additional information can be obtained (e.g., patient or healthcare practitioner refuses to provide additional information; lost to follow-up after demonstration of due diligence with follow-up efforts).
- The patient dies or is lost to follow-up.

All SAEs assessed as unrelated to study drug(s) will be followed until resolution or until the last Safety Follow-up Visit (Section 5.5), whichever is earlier. In the case where an unrelated SAE has not completely resolved by the Safety Follow-up Visit 2 (or 100 [\pm 7]) days after the last dose of study treatment), the final outcome of these ongoing unrelated SAEs will be captured as "Not Recovered/Not Resolved" or "Recovering/Resolving", whichever is applicable.

8.9 Disease Recurrence and Death due to Disease Recurrence – Not Reportable as an AE or SAE

It is anticipated that during this study a proportion of patients will experience disease recurrence prior to study discontinuation. In some patients this may result in hospitalization or death. Such events leading to hospitalization or death of a study patient are typically considered “serious,” requiring submission of an SAE report. However, because disease recurrence is an endpoint for this study, reporting the term “disease recurrence” as either an AE or SAE is not necessary. Signs and symptoms with no principal clinical manifestation related to disease recurrence, may be considered as “disease recurrence” without a requirement to report it as an AE or SAE.

For all SAEs assessed as clinical manifestations associated with fatal disease progression, the following criteria will apply:

- Seriousness Criteria cannot equal Death
- Severity cannot equal Grade 5
- Outcome = Ongoing at time of Death

Deaths that are attributed solely to disease recurrence by the Investigator should not be reported as SAEs.

However, if there are separate identifiable clinical manifestations of the disease recurrence that the Investigator is unsure that the events are attributed solely to disease recurrence, e.g., pleural effusion or weight loss, these manifestations are reportable as AEs. Such an event should be recorded on the AE CRF and, if the event meets any of the “serious” criteria, it must also be reported on the SAE form.

8.10 Adverse Events of Special Interest

The AE listed below is considered an AESI. Regardless of the assessment of whether the AESI is serious or nonserious, all AESIs are required to follow the timeline for SAE reporting (within 24 hours as described in Section 8.7) from the sites to Nektar Drug Safety: [contact].

- CVA events (any grade; CVA Management Guidelines are provided in [Appendix 6](#))

8.11 Immune-mediated Adverse Events and Other Monitored Events

Immune-mediated AEs are AEs consistent with an immune-mediated mechanism or immune-mediated component for which non-inflammatory etiologies (e.g., infection or tumor progression) have been ruled out. Immune-mediated AEs can include events with an alternate etiology which were exacerbated by the induction of autoimmunity. Investigators should use clinical judgment characterizing an AE as immune-mediated, including the requirement for steroid treatment, and are encouraged to rule out neoplastic, infectious, metabolic, toxic, or other

etiologies to the extent possible, before characterizing an event as immune-mediated. Information supporting the assessment of immune-mediated AEs will be collected on the CRF.

Additional information may also be collected on immune-mediated adverse events.

8.12 Additional Information Collected for Adverse Events Primarily Related to Bempegaldesleukin

Additional information may also be collected on select AEs primarily related to NKTR-214, including bempegaldesleukin (e.g., capillary leak syndrome and cytokine release syndrome).

8.13 Pregnancy Tests/Pregnancy

8.13.1 Pregnancy Tests

Serum or urine pregnancy tests will be performed on WOCBP during according to the Schedule of Events (Section 1.2). Urine pregnancy tests should have a minimum sensitivity of 25 IU/L or equivalent units of HCG. A negative pregnancy test result must be obtained within 24 hours before the administration of the study drug(s).

A pregnancy test does not need to be performed on women who are postmenopausal (see [Appendix 4](#)).

8.13.2 Pregnancy

8.13.2.1 Pregnancies in Female Patients

The Sponsor must be notified immediately without undue delay, under no circumstances later than 24 hours following knowledge of the initial report and any follow-up reports of a female patient becoming pregnant during the course of the study and for 5 months after the last dose of nivolumab. All reports should be submitted via the Pregnancy Notification Form. Pregnancy, although reportable, is not considered an AE/SAE unless a female patient experiences signs or symptoms of pregnancy complications; however, the contact information for pregnancy reporting is the same as for SAE reporting and listed in Section 8.7. Female patient(s) who become pregnant will be followed until the outcome of the pregnancy is known. Pregnancy follow-up should describe the outcome of the pregnancy, including any voluntary or spontaneous termination, details of the birth, and the presence or absence of any congenital abnormalities or birth defects in the offspring.

If a female patient becomes pregnant, administration of the study drug(s) must be discontinued immediately.

If, for whatever reason, the pregnancy has ended, confirmed by negative serum pregnancy test, treatment may be resumed at the discretion of the Investigator (at least 3 weeks and not greater than 6 weeks after the pregnancy has ended) following approvals of the patient and IRB/IEC, as applicable.

8.13.2.2 Pregnancies in Female Partners of Male Patients

Any pregnancy occurring up to 7 months after the last dose of nivolumab in a female partner of a male patient must be reported to the Sponsor. The Sponsor must be notified immediately without undue delay, under no circumstances later than 24 hours following knowledge of the initial report and any follow-up information. All reports should be submitted via the Pregnancy Notification Form. In order for the Sponsor or designee to collect any pregnancy surveillance information, the pregnant patient or partner must sign an ICF (see Section 12.2).

Pregnancy, although reportable, is not considered an AE/SAE unless a female partner of male patient experiences signs or symptoms of pregnancy complications; however, the contact information for pregnancy reporting is the same as for SAE reporting and listed in Section 8.7. Attempts should be made to collect and report details of the course and outcome of any pregnancy in the partner of a male patient exposed to study drug with the authorization from the pregnant partner. Pregnancy follow-up should describe the outcome of the pregnancy, including any voluntary or spontaneous termination, details of the birth, and the presence or absence of any congenital abnormalities or birth defects in the offspring.

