Refer to the Schedule of Events (Section 1.2) for data to be collected at the time of treatment discontinuation and follow-up and for any further evaluations that can be completed.

In the case of pregnancy, the Investigator must immediately, within 24 hours of awareness of the pregnancy, notify the Sponsor of this event. If a female patient becomes pregnant, administration of the study drug(s) must be discontinued immediately. Refer to Section 8.13.2 (Pregnancy).

All patients who discontinue study treatment should comply with protocol-specified follow-up procedures as outlined in Section 1.2. The only exception to this requirement is when a patient withdraws consent for all study procedures including post-treatment study follow-up or loses the ability to consent freely (i.e., is imprisoned or involuntarily incarcerated for the treatment of either a psychiatric or physical illness).

If study treatment is discontinued prior to the patient's completion of the study, the reason for the discontinuation must be documented in the patient's medical records and entered on the CRF page.

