12.2 Written Informed Consent

Written documentation of informed consent must be obtained from each patient or (if permitted by the local health authority) a patient's legal representative before entering the study. Patients will be informed of the nature of the study, and the ICF must be presented to each patient in the language in which the patient is fluent.

Informed consent will be obtained from and documented for each patient prior to the conduct of any protocol-specific procedures. Signed and dated ICFs will be retained by the Investigator with the study records. Each patient will be given a copy of the signed and dated ICF.

Any pregnancy that occurs in a study patient or the female partner of a male study patient should be reported to the Sponsor or designee. For the Sponsor or designee to collect any pregnancy surveillance information, the pregnant patient or partner must sign an ICF for disclosure information. Information on this pregnancy will be collected on the Pregnancy Surveillance Form.

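### The partner-pregnancy window runs only from the last nivolumab dose, so for an Arm A man kept on bempegaldesleukin alone it can close before his last dose

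*Protocol*

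**What the plan says.** Section 8.13.2.2 of the protocol makes partner-pregnancy reporting mandatory within a stated window, "Any pregnancy occurring up to 7 months after the last dose of nivolumab in a female partner of a male patient must be reported", and attaches a 24-hour deadline. The parallel rule for female patients (8.13.2.1) also counts from nivolumab, for 5 months, but it expressly covers the course of the study as well. The partner rule has no such words.

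Four other places bear on partner pregnancies:

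- Section 5.12: "In the case of pregnancy, the Investigator must immediately, within 24 hours of awareness of the pregnancy, notify the Sponsor of this event". No closing date is given and partners are not named. The text then turns to a female patient who becomes pregnant and sends the reader to Section 8.13.2.
- Section 12.2: "Any pregnancy that occurs in a study patient or the female partner of a male study patient should be reported", with no deadline and no window.
- A later sentence of 8.13.2.2 asks for attempts to collect and report details of "any pregnancy in the partner of a male patient exposed to study drug".
- 8.13.2.2 also says that a partner's pregnancy "is not considered an AE/SAE unless a female partner of male patient experiences signs or symptoms of pregnancy complications". Section 8.7 then takes over for serious events: those with onset within 100 (±7) "days after the last dose of all study treatment(s) will be reported to Nektar Therapeutics Drug Safety immediately", and later ones "that are assessed by the Investigator as related to study drug(s) will also be reported to Nektar Therapeutics Drug Safety within 24 hours".

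On dosing, Sections 5.3.2.2 and 5.12.1 allow an Arm A patient to continue bempegaldesleukin alone once nivolumab is permanently stopped. Section 5.3 caps Arm A at 17 cycles and lets delayed cycles run past 1 year. Inclusion Criterion 11d and Appendix 4 set the male precautions at bempegaldesleukin treatment plus 3 months, and Appendix 4 describes that point as the end of relevant systemic exposure.

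**The concern.** The exposure that drives the male precautions is bempegaldesleukin, but the reporting clock is tied to the other drug. When both drugs stop together this does no harm, because 7 months after nivolumab outlasts 3 months after bempegaldesleukin. When nivolumab stops early and bempegaldesleukin continues, the clock starts while the man is still being dosed with the investigational agent, and can run out before he finishes.

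A site that applies the specific partner rule could then treat an uncomplicated partner pregnancy as outside the mandatory 24-hour window, although the man is still on bempegaldesleukin or within the 3 months that the protocol itself counts as exposure. What could be lost is prompt, complete reporting of partner pregnancies exposed to an investigational drug. No endpoint, alpha level, power figure or efficacy analysis depends on it.

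**Working it through.** **Inputs.** Arm A cycle length 21 days and maximum 17 cycles (Sections 5.3 and 5.3.2.2). Minimum spacing between doses 18 days (5.3.2.2). Partner window 7 months after the last nivolumab dose (8.13.2.2). Male exposure to 3 months after bempegaldesleukin (Inclusion 11d, Appendix 4). SAE window 100 (±7) days after the last dose of all study treatment (8.7). Conversions: 7 months = 7 × 365.25/12 ≈ 213 days; 3 months ≈ 91 days.

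**The plan's own figure.** 17 × 21 = 357 days, which agrees with the stated treatment length of approximately 1 year.

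**Timeline for a man who reaches Cycle 17 without delays.**

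- Cycle k Day 1 falls on day 1 + 21(k − 1), so Cycle 17 is day 1 + 336 = 337.
- The exposure period ends at 337 + 91 = day 428.
- With the last nivolumab dose at Cycle k, the partner window ends on day 1 + 21(k − 1) + 213 = 214 + 21(k − 1).

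| Last nivolumab cycle | Window ends (day) | Relative to last bempegaldesleukin dose (day 337) | Relative to end of exposure (day 428) |
|---|---|---|---|
| 1 | 214 | 123 days before | 214 days before |
| 6 | 319 | 18 days before | 109 days before |
| 7 | 340 | 3 days after | 88 days before |
| 11 | 424 | 87 days after | 4 days before |
| 12 | 445 | 108 days after | 17 days after |

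**The same result by length of bempegaldesleukin-only treatment.** Let n be the number of bempegaldesleukin-only doses after the last nivolumab dose, so that the last dose falls 21n days later.

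- The window closes before the last dose if 21n > 213. 21 × 10 = 210 is not enough and 21 × 11 = 231 is, so n must be at least 11.
- The window closes before exposure ends if 21n + 91 > 213. n = 5 gives 196 and n = 6 gives 217, so n must be at least 6.

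A man who has one nivolumab dose and stops bempegaldesleukin at Cycle 6 (n = 5) has no gap.

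**Sensitivity.**

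- *Calendar months.* Real calendar months were added for each of the 1,461 first-dose dates from 1 January 2021 to 31 December 2024. The thresholds are Cycle 6 and Cycle 11 for every date. The gap before the last dose is 121–124 days for Cycle 1 and 16–19 days for Cycle 6. The gap before exposure ends is 211–216 days for Cycle 1 and 1–6 days for Cycle 11.
- *Shortest permitted spacing.* With every dose 18 days apart, 18n > 213 needs n ≥ 12 (18 × 12 = 216), so the first threshold falls from Cycle 6 to Cycle 5. 18n + 91 > 213 needs n ≥ 7 (126 + 91 = 217), so the second falls from Cycle 11 to Cycle 10.
- *Delays.* Delays while on bempegaldesleukin alone push the last dose later and widen the gap.

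**The SAE route.** 337 + 100 = day 437 (430 to 444). This passes the end of exposure at day 428, but it applies only when the pregnancy has complications that meet the serious criteria.

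**The case against.** The strongest reply is that the protocol still asks for these reports. Section 12.2 names partners and has no end date. The opening sentence of the pregnancy paragraph in Section 5.12 is an unconditional 24-hour duty that is not limited to patients; the narrowing to female patients comes only in the next sentence, and the cross-reference goes to 8.13.2, which covers both patients and partners. Section 8.13.2.2 itself asks for follow-up of partners of exposed men without a time limit. This stands far enough to rule out any claim that the protocol is silent. It does not restore the rule. Section 12.2 is an undated recommendation placed in the consent section. The 5.12 sentence sits under patient treatment discontinuation and leads back to the section holding the short window. The follow-up sentence in 8.13.2.2 asks only for attempts. The SAE route misses an uncomplicated pregnancy.

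The second reply is that the case is rare, and this stands. Section 5.12.1 by default stops all assigned drugs. A Grade 3 or 4 infusion reaction during or after nivolumab stops both. Continuing requires toxicity attributed to nivolumab and not to bempegaldesleukin, with the criteria to resume met. Men must use condoms. The 123- and 214-day figures are extremes: one nivolumab dose followed by 16 bempegaldesleukin-only cycles.

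It can also be said that this is a drafting inconsistency and not a design fault. That describes the size of the repair fairly, but the rule as written gives the wrong result in a situation the protocol expressly allows.

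**Conclusion.** The concern holds and is minor. The dated, mandatory partner window can close before the last bempegaldesleukin dose, by 18 to 123 days, when the last nivolumab dose is at Cycles 1 to 6. It can close before the protocol's own male exposure period ends, by 4 to 214 days, when the last nivolumab dose is at Cycles 1 to 11. From Cycle 12 there is no gap. These figures assume that the man reaches Cycle 17 on undelayed 21-day cycles. More generally, the two gaps need at least 11 and at least 6 bempegaldesleukin-only cycles respectively, and dosing at the 18-day minimum moves each threshold one cycle earlier.

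What is wrong is the anchor and the disagreement between Sections 8.13.2.2, 5.12 and 12.2. The documents give no rate of stopping nivolumab alone, so the number of men affected is unknown and probably very small.

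**What to change.** In Section 8.13.2.2, require reporting of any partner pregnancy during study treatment and up to the later of 7 months after the last nivolumab dose and 3 months after the last bempegaldesleukin dose. For a man reaching Cycle 17 on schedule this adds 4 to 214 days when the last nivolumab dose is at Cycles 1 to 11, and nothing from Cycle 12.

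A simpler wording is 7 months after the last dose of all study treatment. For the same man that runs to 337 + 213 = day 550, which is 550 − 428 = 122 days beyond the 3-month exposure period.

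Whichever is chosen, Sections 5.12 and 12.2 should refer to that window and its 24-hour deadline, and 5.12 should say whether partners are covered. The cost is one sentence, two cross-references and at most a few extra pregnancy reports.
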